7.1. Discontinuation of Study Treatment

In rare instances, it may be necessary for a subject to permanently discontinue (definitive discontinuation) study treatment. If a subject discontinues study drug administration after randomization (Visit 3), the subject will be encouraged to return for all subsequent on-site visits as listed in the SoA (i.e., Visits 4, 5, 7, 9, 11, 13, 14, 15, and 16). If the discontinued subject chooses to not return for on-site visits, study personnel should make every effort to conduct the Early Termination (ET) visit and ask the subject to return 6 weeks after the last dose of the study drug for the final safety follow-up visit (see Section 1.3). If a subject discontinues study drug administration before randomization, no further assessments will be conducted.

The reasons for permanent discontinuation of study treatment at any time during the study include but are not limited to the following:

- Safety reasons, either at the discretion of the Investigator or at the subject's request.
 - In particular, subjects can be discontinued from study treatment if they develop severe complications of celiac disease that require intensive treatment (e.g., RCD-I or RCD-II, jejunitis, perforation).
 - Malignancy
 - Active TB
 - A serious opportunistic infection
 - Pregnancy (female subjects)
 - Anaphylaxis or severe hypersensitivity reactions after the initial injection(s)
- Significant protocol violations (e.g., noncompliance with study procedures), at the discretion of the Sponsor
- The use of prohibited therapy that may interfere with the study assessment and analysis (Section 6.5.1). The Investigator is required to report all such information on the CRF and decide, upon discussion with the Sponsor, whether the subject is to be discontinued from study treatment.

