8.4.1. Time Period and Frequency for Collecting AE and SAE Information

All AEs and SAEs will be collected from the signing of the ICF through the final visit (Visit 16) as specified in the SoA (Section 1.3).

TEAEs will be collected from the first post-randomization dose of the study drug administration at Visit 3 through the final visit (Visit 16) as specified in the SoA (Section 1.3). The AEs and SAEs reported during the screening and single-blind placebo run-in periods will be reported separately from the TEAEs.

All SAEs will be recorded and reported to the sponsor or designee immediately upon observing or learning of the event and under no circumstance should this exceed 24 hours, as indicated in Appendix 10.2. Information about the SAE should be as complete as possible and include causality. The Investigator will submit any updated SAE data to the sponsor within 24 hours of it being available.

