10.2.1. Definition of AE

AE Definition

• An AE is any untoward medical occurrence in a patient or clinical study subject, temporally associated with the use of study drug, whether or not considered related to the study drug.• NOTE: An AE can therefore be any unfavorable and unintended sign (including a clinically significant abnormal laboratory finding), symptom, or disease (new or exacerbated) temporally associated with the use of study drug.• A treatment-emergent AE (TEAE) is defined as an AE that occurs from the first dose of post-randomization study drug administration through the end of the study.

Events Meeting the AE Definition

• Any abnormal laboratory test results (hematology, clinical chemistry, or urinalysis) or other safety assessments (e.g., ECG, radiological scans, vital signs measurements), including those that worsen from baseline, considered clinically significant in the medical and scientific judgment of the Investigator (i.e., not related to progression of underlying disease).• Exacerbation of a chronic or intermittent pre-existing condition including either an increase in frequency and/or intensity of the condition.• New conditions detected or diagnosed after study drug administration even though it may have been present before the start of the study.• Signs, symptoms, or the clinical sequelae of a suspected drug-drug interaction.• Signs, symptoms, or the clinical sequelae of a suspected overdose of either study drug or a concomitant medication. Overdose per se will not be reported as an AE/SAE unless it is an intentional overdose taken with possible suicidal/self-harming intent. Such overdoses should be reported regardless of sequelae.• The signs, symptoms, and/or clinical sequelae resulting from lack of efficacy will be reported as AE or SAE if they fulfil the definition of an AE or SAE. Also, “lack of efficacy” or “failure of expected pharmacological action” also constitutes an AE or SAE.

Events NOT Meeting the AE Definition

- Any clinically significant abnormal laboratory findings or other abnormal safety assessments which are associated with the underlying disease, unless judged by the Investigator to be more severe than expected for the subject's condition.
- The disease/disorder being studied or expected progression, signs, or symptoms of the disease/disorder being studied, unless more severe than expected for the subject's condition.

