8.2 General Statistical Considerations

Single-blind placebo run-in period is defined as a period for 4 weeks, starting at visit 1.

Treatment emergent period is defined from the first dose of double-blind study drug at visit 3 until the last dose of double-blind study drug + 42 days (i.e., to the end of 4-week safety follow-up period).

Post-treatment period is defined from the end of treatment emergent period.

All outputs are summarized by treatment and visit, if applicable.

Outputs will generally use the following header structure (label and order):

Placebo	PRV-015 100 mg	PRV-015 300 mg	PRV-015 600 mg
N = xx	N = xx	N = xx	N = xx

Total of PRV-015 groups is added for safety and baseline outputs or where relevant in the following way:

Placebo	PRV-015 100 mg	PRV-015 300 mg	PRV-015 600 mg	Total PRV-015
N = xx	N = xx	N = xx	N = xx	N = xx

All statistical tests will be two-sided at the 0.05 level of significance without multiplicity adjustment. In addition to the inferential statistics, 95% confidence intervals will be constructed.

Various covariates will be included in the models and will be retained in the respective models regardless of their significance or lack thereof. The list of variables to be included is described in detail in the following sections.

SAS codes provided in the appendix 11.4 may be modified based on statistical considerations, without requiring SAP amendment.

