8.7.2 Adverse Events

Adverse Events (AEs) and serious adverse events (SAEs) are collected from the signing of the ICF until final visit (Visit 16) and will be classified by System Organ Classes (SOC) and Preferred Terms (PT) using the latest MedDRA dictionary applicable at the time of database lock.

Treatment-emergent adverse events (TEAEs) are collected from the first dose of double-blind study drug until the last dose of double-blind study drug + 42 days. The AEs and SAEs reported during the screening period (those which started after the first screening visit and ended before the start of run-in period or ongoing at the time of run-in period) and single-blind placebo run-in period AEs and SAEs (those which started after visit 1 (first run-in period visit) and ended before the start of double-blind randomized treatment period or ongoing) will be reported separately from the TEAEs.

AEs reported during post-treatment period, i.e. starting at the end of treatment emergent period will be summarized by System Organ Classes (SOC) and Preferred Terms (PT).

Injection site reactions are those identified programmatically using the MedDRA High Level Term of "Injection site reactions".

Adverse Events of Special Interest (AESI) are (1) severe opportunistic infections and (2) hypersensitivity reactions of at least moderate severity. AESI will be programmatically identified for summarization based on the criteria below using MedDRA Preferred Term or Standardized MedDRA Queries (SMQ) (narrow) which also meet severity/seriousness criteria in the eCRF:

Table 3 AESI Criteria

AESI Category	eCRF AE page	MedDRA Search Terms
Severe opportunistic infections	"Severe" or Serious noted in eCRF	PT included in SMQ (narrow) of Opportunistic infections (SMQ) (20000235)
Hypersensitivity reactions of at least moderate severity	"Moderate", "Severe", or Serious noted in eCRF	PT contains "Hypersensitivity" or "hypersensitivity" OR PT included in SMQ (narrow) of • Anaphylactic reaction (SMQ) (20000021) • Hypersensitivity (SMQ) (20000214) • Severe cutaneous adverse reactions (SMQ) (20000020) • Drug reaction with eosinophilia and systemic symptoms syndrome (SMQ) (20000225) • Angioedema (SMQ) (20000024)

An overall summary table of treatment-emergent adverse events will be produced and will present the number and proportion (%) of subjects in each treatment group who have at least one adverse event in the following categories:

- TEAE

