- Blood samples for PK and ADA analyses should be collected before study drug administration (baseline) and at each visit before dosing (trough). The exact time and date of sample collection must be recorded. ADA analysis includes neutralizing antibodies (NAb). The anti-tTG and anti-DGP antibody tests at the screening visit will include both IgA and IgG. At all other visits, only anti-tTG IgA and anti-DGP IgA will be
- 10. Blood samples for biomarker analyses should be taken prior to study drug administration. The time and date of these samples must be accurately recorded. 11. The study drug administered at Visits 1 and 2 (single-blind run-in period) is placebo for all subjects.
- The baseline EGD and biopsy can be performed within 12 days before Visit 2.
- 13. The final EGD and biopsy can be collected within 7 days before Visit 15. A final or early termination EGD and biopsy are required for all subjects. Subjects with early termination should undergo the EGD and biopsy unless a medical condition precludes it, at the Investigator's discretion.
- 14. Subjects are required to answer the stool frequency question (stools of Type 6 or 7 on BSFS) daily before bedtime in the eDiary.
- 15. The CeD PRO is captured daily in the eDiary after the last meal of the day before the subject goes to bed.
- Subjects are instructed to record PGIC and PGIS every other week in the eDiary.
- 17. Treatment-emergent adverse events are collected from the first dose of the post-randomization study drug administration (Visit 3) through the final visit. Between signing the informed consent form and the first dose of study drug (including the single-blind run-in period), only AEs related to study procedures and SAEs will be recorded.

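### The SAP closes the treatment-emergent period 42 days after the last dose, an unlisted departure from the protocol that leaves later events in subjects who stop drug but stay in follow-up out of every SAE, AESI and death table

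*SAP*

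**What the plan says.** **Where the period ends.** SAP 8.2 runs the treatment-emergent period from the first double-blind dose "until the last dose of double-blind study drug + 42 days (i.e., to the end of 4-week safety follow-up period"; the bracket equates the cut with the end of the safety follow-up. SAP 8.7.2 repeats the cut for TEAEs. Anything later belongs to a separate post-treatment period.

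Protocol 10.2.1 defines a TEAE as "an AE that occurs from the first dose of post-randomization study drug administration through the end of the study". Protocol 8.4.1 has TEAEs collected from the Visit 3 dose to Visit 16. Footnote 17 of the schedule, in Protocol 1.3 and again in SAP 11.1, reads "Treatment-emergent adverse events are collected from the first dose of the post-randomization study drug administration (Visit 3) through the final visit".

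**Who stays in the study.** For a subject who stops drug after randomisation, Protocol 7.1 says "the subject will be encouraged to return for all subsequent on-site visits", up to Visit 16. A subject who declines is offered an early termination visit and a final safety visit six weeks after the last dose. SAP 8.2.4 repeats both routes.

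**What is tabulated.** SAP 8.7.2 collects AEs and SAEs to Visit 16. For the later period it says "AEs reported during post-treatment period, i.e. starting at the end of treatment emergent period will be summarized" by SOC and PT, and nothing more. The other post-randomisation tables (serious, AESI, severe, fatal, related, leading to discontinuation) and the risk differences are for treatment-emergent events. The only SAE tables that are not treatment-emergent cover screening and run-in, and the only post-randomisation AE listings named are of TEAEs.

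**How differences are handled.** Protocol 9.4 requires differences between protocol and SAP to be documented in the SAP. SAP 8.10 lists six changes, none on the TEAE window.

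**The concern.** The SAP presents its cut as equivalent to the end of follow-up, so a reader would not expect it to remove anything. For a subject who stops drug early and keeps attending, it removes weeks or months of collected safety data from the treatment-emergent tables.

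Treatment-emergent SAEs and AESIs are declared secondary safety endpoints (Protocol 3, SAP 3.2), so the choice of window changes what those endpoints count. A severe opportunistic infection or a death on day 50 after the last dose, in a subject still attending visits, would enter no planned SAE, AESI or death table. SAEs during the placebo run-in have a table of their own; SAEs arising more than 42 days after stopping active drug do not. Protocol 7.1 names malignancy, active TB, serious opportunistic infection and severe hypersensitivity among the reasons for stopping, so later events in subjects who stop are of interest.

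**Working it through.** **Inputs**

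- Treatment-emergent end: last-dose day + 42 (SAP 8.2, 8.7.2).
- Last planned dose: Visit 14, Day 155, window ±2 days (schedule of activities).
- Final visit: Visit 16, Day 197, window ±7 days (schedule of activities).
- Earlier dosing days: Visit 3 Day 1, Visit 4 Day 15, then every 14 days.

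**Step 1. Reproduce the SAP's equality.** For a completer on nominal days, 155 + 42 = 197, which is Visit 16. For a subject who stops and takes the six-week final visit, the visit falls 6 × 7 = 42 days after the last dose. The statement holds at nominal days for both.

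**Step 2. Subjects who stop drug and attend through Visit 16.** With last dose on day d, the collected days outside the window are

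197 − (d + 42) = 155 − d.

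| Last dose | Day d | Window closes (d + 42) | Days outside (155 − d) | Share of the 196 days from Day 1 to Day 197 |
|---|---|---|---|---|
| Visit 3 | 1 | 43 | 154 | 78.6% |
| Visit 4 | 15 | 57 | 140 | 71.4% |
| Visit 7 | 57 | 99 | 98 | 50.0% |
| Visit 9 | 85 | 127 | 70 | 35.7% |
| Visit 11 | 113 | 155 | 42 | 21.4% |
| Visit 13 | 141 | 183 | 14 | 7.1% |
| Visit 14 | 155 | 197 | 0 | 0.0% |

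The Visit 16 window moves each count of days outside by up to 7 in either direction.

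**Step 3. Completers, visit windows only.** The last dose falls on Days 153 to 157 and Visit 16 on Days 190 to 204. The shortest interval is 190 − 157 = 33 days and the longest 204 − 153 = 51 days. In the extreme case 51 − 42 = 9 days lie outside. With an early Visit 16 the 42 days run past the visit and nothing is excluded.

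**Step 4. Follow one event through the tables.** Take an SAE on day 50 after the last dose in a subject who stopped at Visit 9: 85 + 50 = Day 135, before Visit 16.

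- Protocol 10.2.1: a TEAE, hence a treatment-emergent SAE.
- SAP 8.2: post-treatment, because 135 > 127.
- SAP 8.7.2: one row in the post-treatment SOC/PT summary. It is absent from the SAE, severe, AESI and fatal tables, from the severe, SAE and AESI risk differences, and from the named TEAE listings.

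**The case against.** The strongest reply is that the SAP was invited to set such a rule. The protocol's summary of changes takes the handling of delayed TEAEs in subjects who stop treatment out of section 8.4.1 and leaves it to the SAP, and Protocol 9.4 bases the final analyses on the SAP. A window tied to the last dose is a legitimate choice. This stands, and so making the protocol window the main analysis would be a preference. It does not cover the unlisted difference or the bracketed statement, which presents the cut as changing nothing.

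Second, Protocol 8.4.1 and footnote 17 speak of collection, and the SAP's schedule reproduces the protocol's. Only Protocol 10.2.1 is a definition. That is fair, but one conflicting definition is enough to require reconciliation.

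Third, the events are not lost. SAP 8.2 presents outputs by treatment where applicable, so the post-treatment summary should be by arm. Disposition shows study discontinuation with reason. The DMC meets on any death. A reader might infer that late SAEs and deaths go unreported; the documents do not support that. What is missing is their identification as serious, fatal or AESI.

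Other stronger readings also fail:

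- **That the equality holds only for a completer seen exactly on time.** It also holds at nominal days for subjects on the six-week final-visit route.
- **That the table of TEAEs leading to discontinuation is depleted.** An event more than 42 days after the last dose would not normally be why that drug was stopped, so the table loses essentially nothing.
- **That the protocol's three-month contraception and death-record provisions set a risk period which 42 days cuts short.** They do not define an AE window, and the protocol's own TEAE definition gives a nominal completer only 42 days after the last dose.
- **That subjects who stop mostly do so for safety reasons.** The documents do not say so, and Protocol 7.1 describes permanent discontinuation as rare.

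**Conclusion.** The point holds, for a limited group. The two documents define the treatment-emergent period differently, the SAP does not declare the difference, and its stated equivalence is untrue for subjects who stop drug and remain in scheduled follow-up. Each such subject has 155 − d collected days outside the window at nominal visit days, from 14 (last dose Visit 13) to 154 (Visit 3 only). Completers lose nothing at nominal days and 9 days at most.

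This rests on the subject attending through Visit 16. The trial-level effect cannot be computed: no discontinuation rate is given, nor any split between the two routes after stopping, and the number affected may be small. The textual mismatch and the tabulation gap are certain; their consequence for the safety results is not. The SAP should be corrected, but nothing here calls for a change to the design or to data collection.

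**What to change.** 1. Reconcile the TEAE definition between Protocol 10.2.1 and SAP 8.2 and 8.7.2, and align footnote 17 in SAP 11.1.
2. Correct the bracketed statement in SAP 8.2. Say that 42 days reaches the final visit at nominal days for completers and for subjects on the six-week route, but not for those who stop drug and stay on the visit schedule.
3. List the change in SAP 8.10.
4. Add by-arm tables and listings of SAEs, AESIs and deaths for the post-treatment period and for the whole post-randomisation period through Visit 16. Either window can be the main one, provided both are shown.

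The data are already collected, so the cost is SAP wording and a few extra tables. The downside is that events long after the last dose are harder to attribute to drug; showing the 42-day window alongside keeps the two kinds of event apart.

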8.2.1 Descriptive Statistics

For continuous variables, the following descriptive statistics will be provided, unless stated otherwise: number of non-missing observations (n), number of missing observations (nMiss), mean, median, standard deviation (SD), minimum, maximum, Q1 and Q3 quartiles. Additional statistics will be provided for PK-related data, including the geometric mean (mean_{geo}) and geometric CV% (CV%_{geo}).

For categorical variables, number of non-missing observations and frequency with percentage per category will be displayed. Denominators for percentages are the number of subjects with non-missing values in the pertinent analysis set and treatment group as appropriate, unless otherwise specified.

The number of missing observations (nMiss) is displayed only if > 0. For continuous variables it is displayed after the number of non-missing observations, for categorical variables it is displayed last in category.

8.2.2 Definition of Derived Variables

8.2.2.1 Patient-reported Assessments Captured in eDiary

CeD PRO Domain Scores

The CeD PRO is captured daily in the eDiary after the last meal of the day before the subject goes to bed. It includes 9 items asking participants about the severity of celiac disease symptoms they may experience each day. Participants are asked to rate their symptom severity on an 11-point (0 to 10) scale; from "not experiencing the symptom" to "the worst possible symptom experience". Symptoms include abdominal cramping, abdominal pain, bloating, gas, diarrhea, loose stool, nausea, headache, and tiredness (Figure 2).

[figure not shown]
Analyses will be performed on all individual domain scores and weekly worst symptom domain scores in the GI symptom domains (Abdominal Symptoms and Diarrhea/Loose Stool domains) and Total GI score (Abdominal Symptoms Domain + Diarrhea/Loose Stool Domain + Nausea item). The Total GI score will be assessed with and without inclusion of the Nausea item.

Daily mean domain score is calculated as sum of daily item scores for all items within a domain divided by number of items in the domain.

Weekly domain scores are based on analysis visit windows (defined below) and calculated as the sum of non-missing daily mean domain scores divided by the number of non-missing scores of a given week. A weekly score is calculated if there are at least 4 non-missing daily scores available. Weekly mean total GI score is calculated as the sum of weekly mean Abdominal Symptoms domain score, Diarrhea and Loose Stools domain score, and Nausea item score divided by 3. The weekly mean total GI domain score without the Nausea item, is calculated as the sum of weekly mean Abdominal Symptoms domain score, Diarrhea and Loose Stools domain score divided by 2. If any of the weekly domains are missing, the total score will be calculated as the average over the remainder non-missing weekly domain scores.

Figure 2. Symptom Domains in the Celiac Disease Patient-Reported Outcome Questionnaire

CeD PRO Symptomatic Days

Symptomatic days will be assessed in terms of the Abdominal Domain, Diarrhea and Loose Stool Domain, and Total GI score of the CeD PRO. A given day is defined as a symptomatic day if any of the domain scores is >0. A day is considered asymptomatic if all of these scores are 0. The number of symptomatic days and asymptomatic days will be derived by month (including baseline) [based on month-based visit windows defined below] and total during the double-blind treatment period (through Week 24).

Weekly Worst Symptom Domain Score in CeD PRO

Weekly worst symptom domain scores will be derived separately for each of the following three domains: 1) Abdominal Domain score, 2) Diarrhea and Loose Stool Domain score, and 3) Total GI score by selecting the worst daily score for all items within each domain for a given week (based on analysis visit windows defined below) and averaging these scores.

BSFS Stools of Type 6 or 7

The BSFS is a pictorial aid to help subjects identify the shape and consistency of their stools during the study (Riegler et al, 2001). The subject will be asked to record the number of stools that have a consistency of Type 6 or 7 (loose stool or entirely liquid) at bedtime daily in the eDiary. On the days in which the subject experiences no such stool (BSFS Type 6 or 7), the subject should record 0 in the eDiary instead of leaving it blank. The sum of weekly stool frequency (sum of the previous 7 days) through Week 24 for stools of BSFS Type 6 or 7 will be calculated, based on the analysis visit windows (defined below). In case of multiple records for stool in one day the latest record in time will be considered.

Baseline Value for Patient-Reported Assessments captured in eDiary

In general, the last non-missing value prior to the first dose of double-blind treatment will be used as the baseline value.

For patient-reported assessments captured in the eDiary, the following definitions of baseline in Table 2 will be used:

Table 2. Definition of Baseline for Patient-Reported Assessments Captured in eDiary

Assessment	Baseline Definition				
CeD PRO (Abdominal domain and other weekly domain scores)	Average of scores from 7 days prior to randomization (e.g., last week of placebo run-in).				
BSFS	Sum of Type 6 or 7 stool experienced over the 7 days prior to the date of first dose of double-blind treatment.				
PGIC/PGIS	Most recent assessment prior to the first administration of double-blind treatment.				
PROACTIVE Dietary Questionnaire	Most recent assessment prior to the first administration of double-blind treatment.				

Visit Windowing (post-baseline) for Patient-Reported Assessments captured in eDiary

Analysis visit windows will be applied for following patient-reported eDiary assessments for postbaseline visits and are described below:

- CeD PRO
- BSFS
- PGIS/PGIC
- Weekly Diet Questionnaire

CeD PRO analysis visit windows (for week-based analysis).

In case of missing visit, the prior visit + 14 days will be taken.

Period	Analysis Visit	Days included in analysis window
Double-blind treatment	Week 2	Days -7 to -1 prior to actual Visit 4 date
Double-blind treatment	Week 4	Days -7 to -1 prior to actual Visit 5 date
Double-blind treatment	Week 6	Days -7 to -1 prior to actual Visit 6 date
Double-blind treatment	Week 8	Days -7 to -1 prior to actual Visit 7 date
Double-blind treatment	Week 10	Days -7 to -1 prior to actual Visit 8 date
Double-blind treatment	Week 12	Days -7 to -1 prior to actual Visit 9 date
Double-blind treatment	Week 14	Days -7 to -1 prior to actual Visit 10 date
Double-blind treatment	Week 16	Days -7 to -1 prior to actual Visit 11 date
Double-blind treatment	Week 18	Days -7 to -1 prior to actual Visit 12 date
Double-blind treatment	Week 20	Days -7 to -1 prior to actual Visit 13 date
Double-blind treatment	Week 22	Days -7 to -1 prior to actual Visit 14 date
Double-blind treatment	Week 24	Days -7 to -1 prior to actual Visit 15 date

CeD PRO analysis visit windows (for month-based analysis of symptomatic days)

Period	Month	Days included in analysis window
Run-in	Baseline	Days -28 to -1 prior to Actual Visit 3 date
Double-blind treatment	1	Actual Visit 3 date (inclusive) through day prior to actual Visit 5 date if available, or Visit 3 date + 28 days (if Visit 5 is missing)
Double-blind treatment	2	Actual Visit 5 date (inclusive) through day prior to actual Visit 7 date if available, or Visit 5 date + 28 days (if Visit 7 is missing) or Visit 7 – 28 days if Visit 5 is missing
Double-blind treatment 3		Actual Visit 7 date (inclusive) through day prior to actual Visit 9 date if available, or Visit 7 date + 28 days (if Visit 9 is missing) or Visit 9 – 28 days if Visit 7 is missing
Double-blind treatment	4	Actual Visit 9 date (inclusive) through day prior to actual Visit 11 date if available, or Visit 9 date + 28 days (if Visit 11 is missing) or Visit 11 -28 days if Visit 9 is missing
Double-blind treatment 5		Actual Visit 11 date (inclusive) through day prior to actual Visit 13 date if available, or Visit 11 date + 28 days (if Visit 13 is missing) or Visit 13 – 28 days if Visit 11 is missing
Double-blind treatment	6	Actual Visit 13 date (inclusive) through day prior to actual Visit 15 date if available, or Visit 13 date + 28

days (if Visit 15 is missing) or Visit 15 – 28 days if
Visit 13 is missing

BSFS analysis visit windows

In case of missing visit, the prior visit + 14 days will be taken.

Period	Analysis Visit	Days included in analysis window				
Double-blind treatment	Week 2	Days -7 to -1 prior to actual Visit 4 date				
Double-blind treatment	Week 4	Days -7 to -1 prior to actual Visit 5 date				
Double-blind treatment	Week 6	Days -7 to -1 prior to actual Visit 6 date				
Double-blind treatment	Week 8	Days -7 to -1 prior to actual Visit 7 date				
Double-blind treatment	Week 10	Days -7 to -1 prior to actual Visit 8 date				
Double-blind treatment Week 12		Days -7 to -1 prior to actual Visit 9 date				
Double-blind treatment Week 14		Days -7 to -1 prior to actual Visit 10 date				
Double-blind treatment Week 16		Days -7 to -1 prior to actual Visit 11 date				
Double-blind treatment	Week 18	Days -7 to -1 prior to actual Visit 12 date				
Double-blind treatment Week 20		Days -7 to -1 prior to actual Visit 13 date				
Double-blind treatment Week 22		Days -7 to -1 prior to actual Visit 14 date				
Double-blind treatment	Week 24	Days -7 to -1 prior to actual Visit 15 date				

PGIS/PGIC analysis visit windows

In general, PGIS/PGIC assessments closest to the target date will be selected; if there are equidistant assessments on either side of the actual visit date, the assessment prior to the visit date will be used.

Period	Analysis Visit	Target Visit Date				
Double-blind treatment	Week 2	Closest to actual Visit 4 date				
Double-blind treatment Week 4		Closest to actual Visit 5 date				
Double-blind treatment	Week 6	Closest to actual Visit 6 date				
Double-blind treatment	Week 8	Closest to actual Visit 7 date				
Double-blind treatment	Week 10	Closest to actual Visit 8 date				
Double-blind treatment	Week 12	Closest to actual Visit 9 date				
Double-blind treatment	Week 14	Closest to actual Visit 10 date				
Double-blind treatment	Week 16	Closest to actual Visit 11 date				
Double-blind treatment	Week 18	Closest to actual Visit 12 date				
Double-blind treatment	Week 20	Closest to actual Visit 13 date				
Double-blind treatment Week 22		Closest to actual Visit 14 date				
Double-blind treatment	Week 24	Closest to actual Visit 15 date				

PROACTIVE dietary questionnaire analysis visit windows

In general, PROACTIVE dietary questionnaire assessments closest to the target date will be selected; if there are equidistant assessments on either side of the actual visit date, the assessment prior to the visit date will be used.

Period	Analysis Visit	Target Visit Date				
Double-blind treatment	Week 2	Closest to actual Visit 4 date				
Double-blind treatment	Week 4	Closest to actual Visit 5 date				
Double-blind treatment	Week 6	Closest to actual Visit 6 date				
Double-blind treatment	Week 8	Closest to actual Visit 7 date				
Double-blind treatment	Week 10	Closest to actual Visit 8 date				
Double-blind treatment	Week 12	Closest to actual Visit 9 date				
Double-blind treatment Week 14		Closest to actual Visit 10 date				
Double-blind treatment Week 16		Closest to actual Visit 11 date				
Double-blind treatment Week 18		Closest to actual Visit 12 date				
Double-blind treatment Week 20		Closest to actual Visit 13 date				
Double-blind treatment	Week 22	Closest to actual Visit 14 date				
Double-blind treatment	Week 24	Closest to actual Visit 15 date				

